#### **7.4.4 Inclusion Criteria**

1. Age 18 years and above with provision of consent.
2. Patients with definite or probable nonalcoholic steatohepatitis based on the results of computed tomography and laboratory tests which have been obtained no more than 90 days prior to randomization with or without type 2 diabetes mellitus and insulin resistance.

#### **7.4.5 Exclusion Criteria**

1. Current alcohol use for a period of 3 consecutive months.  
Patients with heart failure.
2. Anamnestic indication of long-term alcohol use in the past.
3. Patients with acute kidney injury at the time of enrollment.
4. Patients with CKD (Chronic Kidney Disease) or with serum creatinine > 1 mg/dL.
5. Patients with platelet count <100.000/mm^3
6. Patients with severe cases of type 2 diabetes mellitus with HbA1c >11.0 %
7. Pregnancy.
8. Patients with hepatocellular carcinoma.
9. Patients who are not willing to participate in the study.
10. Patients with any form of decompensation at the time of enrolment in the study.
11. Patients with hepatitis C as defined by presence of HCV RNA or antibodies to HCV
12. Hepatitis B as defined by presence of HBsAg
13. Users of medications associated with NASH – tetracycline, amiodarone, tamoxifen, glucocorticoids, anabolic steroids.

#### **7.4.6 Formulations and Mode of Intake**

Subjects will be assigned to take orally twice a day either Lycosome™ formulated phosphatidylcholine chaperone, an essential phospholipid formulation containing 450 mg of phosphatidylcholine, or Lycosome™ formulated phosphatidylcholine chaperone (450 mg) fused with lycopene (7mg), an essential carotenoid. The latter is a novel lycosome formulation of lycopene with enhanced bioavailability developed by Lycotec Ltd (Cambridge, UK). Both formulations will be taken orally, twice a day (morning and evening) for a period of 6 months. The volunteers will be asked to take the study products twice a day after meals.

### **8. STUDY DRUG STORAGE AND ACCOUNTABILITY**

The Principal Investigator and Medical Officer for the study are responsible for ordering, receiving, and tracking inventory; storing, dispensing, and returning study products properly; and, where necessary, labeling of study products prior to dispensing according

to protocol guidelines and good manufacturing practices (GMPs). All study products supplied for the protocol will be accounted for and tracked in a manual or electronic accountability log for the study. Accountability for the study products will be documented from the time of initial receipt through dispensation and final disposal of leftover study products. The accountability log will indicate the date, amounts, batch numbers, and condition upon receipt of all materials received from the supplier. Upon study completion remaining study products will be returned or destroyed as defined by specific Investigator instructions, or other documented instructions. The balance returned or sent for destruction will be recorded in the study accountability log. Quality assurance reviews and inspections of study product accountability documentation will be performed at intervals during the study by the Clinical Monitor. Study products will be stored at the clinical site facility in a locked cabinet.

## **9. STUDY DRUG COMPLIANCE AND ADHERANCE**

Compliance of subjects with the protocol and adherence to product intake will be determined by asking questions of the patients during intermediate and final visits to the clinical site and by random private telephone calls. Subjects with poor adherence to the study protocol will be withdrawn from the study by the Medical Officer.

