**Study Design**

The study is designed as a double-blinded, interventional, randomized clinical study involving patients with NASH. A major research question is whether ingestion of lycopene stabilized with Lycosome™ formulated phosphatidylcholine chaperone can reverse clinical and laboratory manifestations of NASH. Therefore, the primary endpoint of the project is the size of the liver and parameters reflecting lipid accumulation in the hepatic tissue at the end of the interventional period. Changes in the activity of liver-specific enzymes and parameters of lipid homeostasis represent the secondary question since normalization of serum levels of hepatic enzymes represents another important criterion of liver damage and its reversal in NASH. Biochemical parameters in serum specimens will be investigated before commencing the study, at the intermediate time points of 1 month and in the end of the study after 2 months treatment. To assess changed in the liver span Ultrasonography was used before and in the end of the trial.

Subjects will be assigned to take orally once a day either capsules containing 450 mg of regular phosphatidylcholine or 450 mg of the same phospholipid in Lycosome™ formulation with 7 mg of lycopene (Cambridge, UK).

The formulations will be dispensed to the subjects during follow-up visits each month. Monthly visits are planned to determine compliance and adherence to the protocol. A basic medical check-up will be performed and subjects will be asked questions to determine adherence to the protocol during each visit.

Packaging and labeling of the study products will be carried out according to the guidelines of NIH and US Department of Health and Human Services as recommended for biologics and investigational health food products. The formulations will be shipped to the study site in specially designed containers with primary and secondary components. The container closure system will prevent exposure of the investigational products to light, moisture, temperature extremes and air. This packaging system guarantees stability of the product for intended use. Protection from microbial contamination will be provided by maintaining container integrity after the packaging system is sealed. An adequate and validated procedure was used for investigational product manufacture and packaging.

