All individual packages will be labeled with a numerical code. None of the volunteers or trial personnel will be informed of study group assignment for the duration of the study. Unblinding of the results is planned to be performed by an independent statistician who will be hired and assigned to the work at the end of the study period.

Upon arrival at the clinical site the study products will be inspected by the Medical Officer and Clinical Monitor, then placed in a locked room at the clinic. Only the Medical Officer, PI and Clinical Monitor will have access to the products during the study period. Each subject will be given a one month supply of the study product at the "zero" time point of the study and then subsequently for each month of the study period following verification of compliance with the study protocol.

Total study duration is six months with a medical check-up for each volunteer at the "0" time point of the study as well as at 1st month and at the 2nd, the end of the interventional period.

During the medical check-ups each volunteer will be subjected to thorough clinical and laboratory investigation. Clinical investigation will include reading the vital signs, determination of body mass index, anthropometry, blood pressure measurement and computed tomography (at the initial and final time points of the study). Among laboratory tests will be determination of fasting serum glucose and lipids (total cholesterol, LDL, HDL and total triglyceride

[figure not shown]

levels), determination of ALT and AST levels, alkaline phosphatase, gamma glutamyl transpeptidase, lactate dehydrogenase, total bilirubin, CRP, LDL oxidation and IOD. Moreover, serum lycopene concentration and lycopene isomer profile will be measured at the initial and final points of the interventional period. All volunteers will also be subject to a standard hematological investigation.

Results collected for each volunteer will be stored as both paper files and digital files in Excel format and will be available for access by the Medical Officer, Medical Monitor and PI. To avoid any bias each subject will be given a random computer code containing three numerical characters and three letters. Decoding of the individual results will be carried out by an independent statistician hired for the purpose.

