## **17. STUDY DISCONTINUATION CRITERIA**

### **17.1 Discontinuation of individual research subjects**

Individual research subjects can be withdrawn from the study due to occurrence of adverse effects, volunteer's request (regardless of reason) and non-compliance with the protocol. Volunteers withdrawn from the study will be replaced from the pre-screened pool of volunteers.

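### Adherence is judged only by self-report, with no threshold, yet it triggers withdrawal, replacement and resupply after randomization; count capsules and keep every randomized subject in the primary analysis

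*Protocol*

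**What the plan says.** Section 9 states the method: adherence is determined "by asking questions of the patients during intermediate and final visits to the clinical site and by random private telephone calls". The Study Design part of section 6 agrees: "subjects will be asked questions to determine adherence to the protocol during each visit". Neither place mentions a count of capsules, a cut-off or a definition of poor adherence.

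Three consequences follow from the judgement:

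- Withdrawal (section 9): "Subjects with poor adherence to the study protocol will be withdrawn from the study by the Medical Officer".
- Replacement (section 17.1, which lists non-compliance among the reasons for withdrawal): "Volunteers withdrawn from the study will be replaced from the pre-screened pool of volunteers".
- Resupply (section 6, Study Design): after the first pack, product is given "for each month of the study period following verification of compliance with the study protocol". No other way of verifying compliance is described.

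Two other parts of the protocol bear on exposure, but neither is tied to adherence. Section 8 keeps an inventory log from receipt to disposal, and for product left at study completion "The balance returned or sent for destruction will be recorded in the study accountability log". Section 6 says that "serum lycopene concentration and lycopene isomer profile will be measured at the initial and final points of the interventional period".

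**The concern.** Self-report is a weak measure, and here it carries a strong consequence. Who is withdrawn depends on what subjects admit and on how one officer reads an undefined term. That decision comes after randomization, and the subject is then replaced by someone else. If adherence depends on how the product is tolerated or on whether it seems to work, the subjects who remain are no longer the groups that were randomized.

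Interpretation suffers too. If the result is null, the sponsor will have no quantified intake by arm, so it cannot judge whether the product failed or was not taken. No analysis plan can recover capsule counts that were never recorded, or final assessments that were not made because the subject had been withdrawn.

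**Working it through.** This is mainly a reading of the text. Arithmetic serves only to show scale.

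**1. Is there any objective adherence measure?**

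| Source | What it provides | Can it judge a subject's adherence during treatment? |
|---|---|---|
| Section 9; section 6, Study Design | Questions at visits, random calls | Yes, but by self-report and with no cut-off |
| Section 8 | Inventory log; leftover product at study completion | No. It does not say that subjects bring packs back or that capsules are counted per subject |
| Section 6, serum lycopene | Start and end of the interventional period only | No. The second value comes after all resupply and withdrawal decisions |

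**2. Could a count be taken at planned visits?** Section 6 has monthly visits at which product is dispensed, so a pack could be returned and counted there. Section 7.4.2 instead lists assessments at months 2, 4 and 6, so the visit plan must be reconciled with section 6.

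**3. Is the expected count defined?** Not yet. Section 6 has intake once a day and section 7.4.6 twice a day. Assuming one capsule per intake and a 30-day month, the expected number is 30 × 1 = 30 or 30 × 2 = 60. A subject who took 30 capsules would be at 30/30 = 100% on one reading and 30/60 = 50% on the other.

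**4. Weight of one withdrawal.** Section 6 (Sample Size) has 20 per group and section 13.2 has 40. One subject is 1/20 = 5% or 1/40 = 2.5% of a group.

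**5. Dilution by non-adherence (illustration).** Section 13.2 gives one-sided 2.5% significance and 90% power, but no effect size or SD, so its total of 80 cannot be reproduced. Solving backwards with the normal approximation for two means:

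- Implied standardized difference, 40 per group: d = (1.960 + 1.282) × √(2/40) = 0.725. For 20 per group it is 3.242 × √(2/20) = 1.025.
- Assume that a fraction q of subjects is non-adherent and gains nothing. The effect becomes d(1 − q), and power = Φ[3.242(1 − q) − 1.960].
- The number per group that restores 90% power is 40/(1 − q)², rounded up.

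| q | Argument of Φ | Power | Needed per group |
|---|---|---|---|
| 0 | 1.282 | 90% | 40 |
| 10% | 0.957 | 83% | 50 |
| 20% | 0.633 | 74% | 63 |
| 30% | 0.309 | 62% | 82 |

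The power column holds for any design with 90% power at this significance level. The rates q are assumptions, since the protocol gives none.

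**6. What can serum lycopene show?** In the lycopene arm, the change from start to end reflects uptake. In the control arm it can show only lycopene from outside the study product, because section 7.1 lists common foods that contain it. Even this separation is uncertain: section 6 describes the control as regular phosphatidylcholine, section 7.4.6 as a Lycosome formulation, and the Lycosome Structure text in section 7.2 puts lycopene in the outer layer of the particle.

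**The case against.** The case against is substantial.

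- **The objective measures are not already in hand.** A reader might infer that returned product and serum lycopene are available and simply ignored. The documents do not support this. Section 8 covers study inventory, so a capsule count per subject would be a new procedure. Lycopene at two time points cannot guide withdrawal or resupply, and it cannot show whether control subjects took their capsules. This part of the objection stands in full.
- **The power figures do not measure the flaw.** They show what non-adherence does under assumed rates. Counting capsules restores none of that power. This also stands.
- **Counting does not cure the bias.** Withdrawal and replacement after randomization would disturb the comparison however adherence was measured. This is correct, and it is why the fix must also cover the analysis.
- **Medical staff are blinded**, which limits judgement that deliberately favours one arm. That helps, but adherence can itself depend on the product taken, so selecting on it can still unbalance the groups.
- **The analysis set may be defined in an SAP that is not shown.** The protocol does not say that withdrawn subjects' data are discarded, and a reader should not infer that it does. Even so, withdrawal and replacement are protocol rules, and they determine which final data will exist.
- **The rest is preference, because the two passages on method agree.** They do agree. But the method they state is weak for the decision it drives, and a better one is cheap.

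**Conclusion.** The point holds as a modest improvement. Adherence is assessed by self-report alone, without a threshold, and that assessment leads to withdrawal, replacement and conditional resupply. Followed as written, the protocol lets a subjective decision after randomization shape who is analysed. Each such decision affects 2.5% or 5% of a group, depending on which sample size applies. The protocol gives no basis for predicting how many there will be or in which direction they would bias the result.

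The conclusion rests on the wording of sections 6, 8, 9 and 17.1 and does not depend on the dilution figures. Those require assumed non-adherence rates, no benefit in non-adherers and a true effect that gives 90% power.

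**What to change.** 1. **Section 9: add a capsule count.** Have subjects return their pack at each dispensing visit, record the capsules remaining in the CRF, and report percent taken by arm. First reconcile the once-daily and twice-daily passages (sections 6 and 7.4.6) and the visit schedules (sections 6 and 7.4.2), so that the expected count is defined.
2. **Sections 9 and 17.1: protect the primary analysis.** State that subjects judged poorly adherent stay in the primary analysis in their randomized group, are followed to the final assessment where they agree, and are not substituted in that analysis by replacements. This concerns follow-up and analysis only, not whether a subject goes on taking the product.
3. **Serum lycopene: give it a limited role.** Use the planned baseline and final values as a descriptive exposure check, released only after database lock because they could reveal the arm. They would describe uptake in the lycopene arm and outside lycopene intake in the control arm, not control capsule-taking. Reconcile the descriptions of the control in sections 6, 7.2 and 7.4.6 first.

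The cost is a few minutes per dispensing visit and one CRF field, with no new laboratory tests. Following withdrawn subjects to the end uses the final assessment already planned for them.

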## **10. CONCOMITANT MEDICATIONS**

Patients with concomitant intake of anti-hypertensive, lipid-lowering or any other cardio-vascular drugs will be illegible for the study. Subjects will be allowed to take prescription medication assigned by primary care physician.

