**7. CLINICAL PROTOCOL****7.1 Introduction****Background**

Lycopene is a polycarbon polyunsaturated red pigment from certain fruits and vegetables (tomatoes, papaya, strawberries, red bell pepper and cherries) which belongs to the carotenoid family and has extremely powerful antioxidant properties in vivo and in vitro (1). There is a growing body of clinical evidence that introduction of lycopene into the human diet prevents multiple diseases such as prostate cancer, type 2 diabetes and atherosclerosis. Recent studies indicate that lycopene supplementation deeply affects liver functions (2). In particular, as shown under experimental conditions, lycopene can prevent development of steatohepatitis in rodents (3).

Steatohepatitis, otherwise known as fatty liver disease, is a common pathological condition of liver which is characterized by accumulation of lipids in the hepatic tissue (4). Steatohepatitis accompanies multiple internal diseases such as obesity, type 2 diabetes, insulin resistance and hyperlipidemia and may finally result in liver cirrhosis (5). Although the exact number of patients with steatohepatitis in the world is not precisely defined, this number may approach 250 million patients who suffer from obesity and type 2 diabetes (6). Methods for steatohepatitis treatment are not well defined or standardized as yet. Diet, exercise and antiglycemic drugs are believed to be helpful in management of steatohepatitis, however no specific medication has been proposed as yet (7).

However, there is recent evidence that vitamin E therapy may attenuate steatohepatitis development (8). This suggests that use of antioxidants, including lycopene, may represent a novel strategy in treatment of steatohepatitis (8).

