## **7.4 Study Design**

### **7.4.1 Selection and randomization of volunteers**

Medical personnel from the outpatient clinic of the Institute of Cardiology, Saratov, Russian Federation will be informed about launching the study, its major goal and selection criteria for volunteers. Suitable individuals will be invited for a preliminary check-up (physical and laboratory investigation) during the initial phase of enrolment. All suitable individuals will be re-screened after the wash-out period of the study before the final decision on study enrolment is made.

Randomization of volunteers in the study will be performed using widely accepted methods such as simple randomization and stratified randomization. Briefly, software containing a random number generator will be applied to the database of volunteers. The assigned group will be considered final. The groups will be balanced according to numerical age and gender with special software.

Stratified randomization will be used to enhance the statistical power of the final results and will ensure equality of groups for secondary selection criteria.

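### Diabetes status is not a named balancing factor and the stated tests are unadjusted, in a small trial that enrols patients with and without type 2 diabetes

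*Protocol*

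**What the plan says.** **Who is enrolled.** Section 7.4.4 admits patients "with or without type 2 diabetes mellitus and insulin resistance". Section 7.4.5 removes only the upper end: "Patients with severe cases of type 2 diabetes mellitus with HbA1c >11.0" per cent. Diabetic patients up to 11.0% are therefore eligible beside non-diabetic ones.

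**What the protocol believes about background treatment.** Section 7.1: "Diet, exercise and antiglycemic drugs are believed to be helpful in management of steatohepatitis". It adds that "there is recent evidence that vitamin E therapy may attenuate steatohepatitis development".

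**How the arms are balanced.** Section 7.4.1: "The groups will be balanced according to numerical age and gender with special software". The next paragraph promises stratified randomisation to equalise the groups on secondary selection criteria, but never lists them.

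**How the arms are compared.** Section 13.1 gives t-tests, the Wilcoxon-Mann-Whitney test at a single time point and Fisher's exact test. None adjusts for a covariate.

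**What may be taken on study.** Section 10 opens with an eligibility rule, "Patients with concomitant intake of anti-hypertensive, lipid-lowering or any other cardio-vascular drugs will be illegible for the study" (evidently meaning ineligible), and continues: "Subjects will be allowed to take prescription medication assigned by primary care physician". The exclusion list in 7.4.5, repeated in the Protocol Summary, bars "Users of medications associated with NASH – tetracycline, amiodarone, tamoxifen, glucocorticoids, anabolic steroids".

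**Size.** The Protocol Summary gives 20 per group; Section 13.2 gives 40 per group. The conflict is a separate matter, so both sizes are carried here.

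**The concern.** By the protocol's own account, diabetes accompanies the disease and antiglycaemic treatment may improve it. Diabetes status is thus likely to be related to the outcomes (liver size, hepatic fat, enzymes, lipids) and to which background drugs a subject takes. It is known before randomisation, so it can be balanced by design at almost no cost.

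As written, nothing in the protocol commits the trial to doing so. If the arms happen to differ in their share of diabetics, an unadjusted comparison carries the difference into the estimated effect, where it could add to or mask an effect credited to lycopene. Even when the arms happen to be balanced, leaving a prognostic factor and the baseline value out of the analysis makes the estimate less precise than it need be.

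Stratification factors have to be fixed before the first subject is randomised. That part cannot be deferred to a later analysis plan.

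**Working it through.** **1. The plan's own figure.** Section 13.2 states a one-sided 2.5% level, 90% power and 40 per group, but no effect size or standard deviation, so the number cannot be reproduced forwards. Inverting the usual formula gives the standardised difference that each size would detect:

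d = (z for 2.5% one-sided + z for 90% power) × √(2/n) = (1.960 + 1.282) × √(2/n)

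- n = 40 per arm: d = 0.725
- n = 20 per arm: d = 1.025

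These serve only as a yardstick in step 4.

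**2. Chance imbalance if diabetes is not balanced.** Inputs: n per arm (20 or 40, from the protocol) and diabetes prevalence p (assumed 30-50%). Let X and Y be the numbers of diabetics in the two arms, independent Binomial(n, p). A gap of 20 points or more is |X − Y| ≥ 4 with 20 per arm and |X − Y| ≥ 8 with 40 per arm.

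| p (assumed) | 20 per arm | 40 per arm |
|---|---|---|
| 30% | 0.226 | 0.067 |
| 40% | 0.258 | 0.086 |
| 50% | 0.268 | 0.093 |

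So the chance is about 23-27% and 7-9%. At a prevalence of 20% it is 16% and 3.5%.

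**3. Why not condition on the total number of diabetics.** With equal arms, the difference X − Y has the same parity as the total. Fixing an even total lets a difference of exactly 4 (or 8) count; with an odd total the smallest qualifying difference is 5 (or 9). The hypergeometric results are:

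| Total diabetics, 20 per arm | Chance | Total diabetics, 40 per arm | Chance |
|---|---|---|---|
| 12, 16, 20 (even) | 0.30, 0.33, 0.34 | 24, 32, 40 (even) | 0.09, 0.11, 0.12 |
| 13, 15, 17, 19 (odd) | 0.18, 0.19, 0.20, 0.21 | 25 to 39 (odd) | 0.05 to 0.07 |

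The binomial figures in step 2 average over the total and are the ones to quote.

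**4. What a 20-point gap would do to the contrast.** Shift = imbalance × outcome difference associated with diabetes or its treatment. If that difference is 0.3-0.8 SD (assumed; the protocol gives none), the shift is 0.20 × 0.3 = 0.06 SD to 0.20 × 0.8 = 0.16 SD. Against step 1 that is 8-22% of 0.725 (40 per arm) and 6-16% of 1.025 (20 per arm): not negligible, but not dominant.

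**5. Cost in sparse strata.** Sex (2) × two age bands (2) × diabetes (2) = 8 cells, averaging 40/8 = 5 subjects each in a 40-subject trial and 80/8 = 10 in an 80-subject trial.

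**The case against.** **Diabetes may already be covered.** Section 7.4.1 also promises stratification on secondary selection criteria, and diabetes status appears in the inclusion criteria. A reader might infer from the sentence on age and gender that diabetes is certainly left to chance. The text does not establish that; it shows only that the factor is not named. The probabilities above are therefore conditional on diabetes not being among those criteria.

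**Randomisation already protects the test.** This stands. In a randomised, double-blind trial, chance imbalance is allowed for in the type I error rate and is not systematic bias. What remains is lost precision and a result that is harder to interpret if an imbalance occurs.

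**Adjustment belongs in the analysis plan.** Partly right: a plan not shown here may specify covariates. But Section 13.1 does state its methods, and they are unadjusted. Handling of drug changes as intercurrent events and related sensitivity analyses can properly wait for that plan.

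**Section 10 against the exclusion list.** One might infer a contradiction. The list governs entry and the permission governs enrolled subjects, so both can hold. That a listed drug may be started after randomisation, or an antiglycaemic dose changed, follows from an open permission without a stability condition; the protocol does not say so in words. It is a mismatch to reconcile.

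**Recording.** One might infer that medication changes go unrecorded. Section 15.1 requires a case report form matched to source records, including pharmacy dispensing records, and Section 12.1 captures abnormal findings that need significant added drug treatment. The form's content is not shown, so absence of a medication log cannot be asserted.

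**Vitamin E.** Section 10 covers it only if prescribed; other use is not addressed. The protocol says that it may attenuate the disease and that antiglycaemic drugs are thought to help, which is weaker than saying that they act on it.

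**Stratification does not control later drug changes.** Correct. It balances status at entry only.

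**Conclusion.** The point holds as a design improvement worth making. Diabetes status is a plausible prognostic factor on the protocol's own reasoning and is known at screening, yet it is neither named for balancing nor used in the stated tests.

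If it is not among the undefined criteria, and if prevalence is 30-50%, a gap of 20 points or more has a probability of about 23-27% with 20 per arm and 7-9% with 40 per arm. With an assumed 0.3-0.8 SD outcome difference, a gap of 20 points moves the contrast by 0.06-0.16 SD. Prevalence and outcome difference are both assumptions.

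The consequence is chance imbalance and reduced precision. The documents do not support a claim of systematic bias, of a proven contradiction in the medication rules, or of missing medication records. The mismatch between Section 10 and the exclusion list is a secondary matter of clarification.

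**What to change.** 1. **Section 7.4.1:** name diabetes status (yes/no, from screening) as a balancing factor and list what the secondary selection criteria are. Use coarse age bands, or minimisation, so that cells do not become too thin.
2. **Section 13.1:** compare the endpoints with adjustment for diabetes status and the baseline value of the outcome, for example by analysis of covariance for continuous endpoints.
3. **Secondary, Section 10 and the exclusion list (Protocol Summary and 7.4.5):** reconcile them by stating whether the list also applies after randomisation. Which treatments a subject may receive is for the investigators to decide.
4. **Secondary, data collection:** log starts and changes of antiglycaemic and other liver-active drugs, with dates, at the visits already planned, if the case report form does not already do so.

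The cost is one binary factor in the randomisation software, two covariates in the comparison, a sentence in Section 10 and at most one extra form page. The real downside is sparse strata, about 5 subjects per cell at 20 per arm even with two age bands, which is the reason for coarse bands or minimisation. Balancing will largely remove the imbalance in diabetes status, but not differences that arise from drugs started or changed later; item 4 makes those visible.
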